## 6.7. Compliance and IMP Accountability

Dosing will be performed by trained and qualified personnel designated by the Investigator during the ambulatory visits in the morning. The date and time of IMP dosing will be documented on each dosing day during the outpatient visits. During home dosing periods (including evening dosage), time of IMP and methotrexate dosing should be documented in the patient's Diary. Comments will be recorded if there are any deviations from the planned dosing procedures. A single dose is to be consider as a compliant when all 4 tablets are administered, and administration is without any emesis occurring within 2 hours after IMP administration. A patient is to be considered as a complier with dosing regimen when at least 80 % of the doses are compliant (at least 136 doses). Compliance from days of home dosing will be verified by a designated person taking into account data from the Patient's diary and empty blisters patient brings on the next visit and during phone call visits. On Day 85 subjects will be hospitalized up to Day 86 in the morning due to donation of blood samples for PK analysis in 13 timepoints. Subjects can spend Day 85 night to Day 86 outside of the clinic but it is necessary to return on Day 86 in the morning in order to donate the last sample of blood 24h after morning CPL409116 administration on Day 85. The Sponsor shall supply an adequate quantity of the investigational medicinal product (IMP) and the placebo, both for administration and as a backup, along with the respective certificates of analysis (CoA). The amount of each product should be sufficient to account for any loss resulting from its potential damage or subject's withdrawal.

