- the subject suffers from moderate or severe emesis within 4 hours in two consecutive IMP administrations. If emesis occurs within 4 hours post-dose and is mild or moderate or emesis occurs

after 4 hours post-dose, discontinuation of the subject depends on the Investigator's judgment and decision.

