2.1.2. Secondary endpoints

Clinical Efficacy:

- Proportion of subjects with DAS28-CRP remission at Weeks 4; 8; 12 and 16.
- American College of Rheumatology (ACR)20, ACR 50, ACR 70, and ACR 90 responder rates (Weeks 4, 8 and 12).
- Change from Baseline in the Tender/Painful and Swollen Joint Count (Weeks 4, 8 and 12).
- Change from Baseline in the Physician's Global Assessment (PhGA) of Arthritis (Weeks 4, 8 and 12).

Patient Reported Outcome:

- Change from baseline in the Patient's Assessment of Arthritis Pain (PAAP) VAS and Patient Global Assessment of Arthritis (PtGA, VAS) at Week 4, 8, and 12.
- Change from baseline in the Health Assessment Questionnaire – Disability Index (HAQ-DI) at Week 4, 8, and 12.
- Change from baseline in the SF-36 RAND 8 Domain scores and Physical Component Score (PCS) and Mental component score (MCS) at Week 12.
- Change from baseline in the Functional Assessment of Chronic Illness Therapy Fatigue (FACIT-F) total score at Week 12.

Safety:

Safety and tolerability of CPL409116: vital signs (blood pressure (BP), pulse and temperature), laboratory tests, Adverse Events (AEs) and Serious Adverse Events (SAEs), 12-lead electrocardiogram (ECG):

- Incidence and severity of adverse events, serious adverse events, and withdrawals due to adverse events (Baseline through Week 16).
- Incidence of abnormality in clinical chemistry parameters (Baseline through Week 16).
- Incidence of abnormality in haematological parameters (Baseline through Week 16).
- Change from baseline in blood pressure measurement (Baseline through Week 16).
- Change from baseline in pulse rate measurement (Baseline through Week 16).
- Change from baseline in temperature measurement (Baseline through Week 16).
- Incidences of targeted medical adverse events (Baseline through Week 16).

Pharmacokinetics:

- CPL409116 and metabolite M3 pharmacokinetic variables: $AUC_{(0-6h)}$, C_{max} , T_{max} , $T_{1/2}$ (if possible) and K_{el} (if possible) determined on Day 1, 8, 57 and 85.
- CPL409116 pharmacokinetic variables: C_{0h} , $C_{2.5h}$ determined on Day 29.

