2.2. Study design

This is a 12-week, phase II, multicentre, randomised, double blind, efficacy and safety study of CPL409116 in participants with active rheumatoid arthritis who are taking methotrexate but have an inadequate response to this drug.

Approximately 100 male and female subjects are to be enrolled in the study. Eligible subjects are to be randomized into one of the 4 treatment arms determined in points below:

- 25 are to be randomized to the treatment arm with CPL409116 at a dose of 60 mg BID;
- 25 are to be randomized to the treatment arm with CPL409116 at a dose of 120 mg BID;
- 25 to the treatment arm with CPL409116 at a dose of 240 mg BID;
- 25 to the treatment arm with placebo.

Randomisation ratio is to be: 1:1:1:1. This will be the age-stratified randomisation. In all treatment arms investigated product/ placebo is to be administered orally for 12 weeks in a blinded fashion. In order to maintain the blind and minimize bias, all subjects will receive the same number and types of tablets each day of treatment.

The study consists of 3 phases:

- A Screening phase of up to 4 weeks,
- A double-blind treatment phase (Day 1 to Day 85/86; 12 weeks) with two doses of IMP administration per day (except Day 85 when patients are to ingest only one dose of IMP in the morning and except Day 86 without administration of CPL409116, when the last sample of blood will be collected for PK analysis in the morning),
- A 4 weeks post-treatment follow-up phase up to Week 16 (Day 113). Patients are to come to a study centre two times after the last dose of IMP. According to the schedule assessment in the follow-up period are planned two ambulatory visits and phone calls from clinical centres: Week 14 and 16 (Day 99 and 113 respectively)- an ambulatory visit; Week 13 and 15 (Day 92 and 106 respectively)- phone call from a clinical centre. The end of the study is planned at Week 16 (Day 113).

[figure not shown]

Figure 1. Study design

In the **Screening Period**, patients undergo screening assessments from Day -28 to Day 0. Rolling admission is employed in this study. Patients that fulfil all the inclusion criteria and none of the exclusion criteria will be considered eligible for this study. Subjects must complete all screening procedures and assessments and have test results available prior to the Baseline visit (Visit 2).

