3.1. Analysis populations

The following populations are to be analyzed:

- Full Analysis Set (FAS): All randomized patients.
- Intent to Treat Set (ITT): All randomized patients that received at least 1 dose of IMP (60 mg, 120 mg, 240 mg CPL409116 or placebo) and have completed baseline assessments allowing for calculation of DAS28-CRP score. Subjects will be grouped according to treatment as randomized. This will be the main population used for analysis.
- Per Protocol Set (PP): Patients from the FAS who complete the Treatment Period (Day 85) without a major protocol deviation. Protocol deviations will be determined before unblinding.
- Safety Analysis Set (SS): All patients who receive at least 1 dose of IMP (60 mg, 120 mg, 240 mg CPL409116 or placebo).
- Pharmacokinetic Set (PS) – all patients dosed with CPL409116 with at least 1 PK parameter evaluable.
- Pharmacokinetic Set for parameter calculation (PSPC): All patients dosed with CPL409116 with at least 1 PK parameter evaluable and without any major protocol deviation during Treatment Period thought to interfere with the absorption, distribution, metabolism, and excretion of CPL409116.

The FAS will be used for demographic and other baseline characteristics. The ITT will be the primary analysis set used for all efficacy analyses and the PP will be employed for supportive analyses of the primary and secondary efficacy endpoints. Patients will be included in the treatment group they were randomized to. The SS will be used for all safety analyses and patients will be included in the treatment group based on the treatment they actually received. PS and PSPC will be used for pharmacokinetic analyses, including exploratory pharmacokinetic analyses.

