4.2.6. Treatment exposure and treatment compliance

Drug exposure is the total number of days the patient takes study drug during the overall study period (not including interruptions). Exposure to IMP will be calculated as:

Exposure = (Last IMP dose – First IMP dose) + 1 - sum of interruptions

Extent of exposure will be calculated as a sum of exposures of all patients and expressed in patient-treatment years:

Extent of exposure [patient months] = sum(Exposure)/30.44.

Drug adherence will be assessed based on patient's diary and calculated as:

Drug adherence [%] = Number of compliant doses taken/Number of doses to be taken
100%*

A single dose is to be consider as a compliant when all 4 tablets are administered. Number of doses to be taken is equal to 169 (84 days * 2 + 1).

A patients is to be considered as a complier with dosing regimen when at least 80% of the doses are compliant (136 doses).

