4.6. Handling of withdrawals, missing values and outliers

For the main analyses performed using the ITT and PP populations, data will be analyzed as observed during the study, no imputation rule will be applied.

A sensitivity analysis will be conducted for primary and secondary efficacy endpoints, whereby missing data are imputed using last observation carried forward method (LOCF) for continuous endpoints and non-responder imputation (NRI) method for binary endpoints.

In pharmacokinetic analyses, missing drug concentration data (no value, not available, NA) will be omitted from PK calculations. Drug concentration data below LLOQ will be treated in pharmacokinetic analysis as follows:

- If the concentration below LLOQ is recorded after the last measurable concentration in the dosing interval, then it is omitted from area calculations and elimination phase analysis.
- In other cases the concentration below LLOQ concentration value is set to zero.
- If an entire concentration-time profile below LLOQ, the profile will be excluded from the PK analysis.

For descriptive statistics of drug concentrations and calculation of PK parameters obtained directly from the observed concentrations (including C_{max} , $C_{min,ss}$, $C_{max,ss}$, C_{trough}) values below LLOQ will be set to zero.

A worst-case scenario will be used in the estimation of partial dates such as adverse events, medical history, rheumatoid arthritis history, smoking history or concomitant medications. That is, for an incomplete start date the first day of the month or the first month of the year will be used. For an incomplete stop date the last day of the month or the last month of the year will be used. If an estimated start date of event is earlier than the date of day 1 or the start date is completely missing, day 1 will be used, unless documented data does not allow for this interpretation.

If start date of smoking is completely missing, it will be replaced with the date of 18th birthday. For completely missing stop date of smoking, date when informed consent was signed will be used.

Whenever estimated dates will be calculated, the incomplete date will be listed and the study day will be calculated using the estimated date. These study days will be flagged as estimated in listings with a star (*) symbol.

For other situations regarding missing data not mentioned in this document, missing data will generally not be replaced or imputed.

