4.13. Pharmacokinetic analyses

Analyses will be performed for PS and PSPC populations. Concentration data and calculated PK parameters will be listed for PS population, while data summaries, plots, and inference analyses will be performed in PSPC population. In case PS and PSPC (PS = PSPC) are identical, all analyzes will be performed only in PS analysis set.

[figure not shown]
The following pharmacokinetic parameters will be estimated if data permits: $AUC_{(0-6h)}$, C_{max} , T_{max} , K_{el} and $T_{1/2}$ for CPL409116 and its M3 metabolite, individually for each subject and separately for Days 1, 8, 57, and 85. They will be computed using non-compartmental modelling approach using actual sampling times.

All individual pharmacokinetic parameters described above will be presented in listings and analyzed with descriptive summary statistics including arithmetic mean, geometric mean, median, quantiles Q1 and Q3, standard deviation (SD), coefficient of variation (CV), minimum and maximum. Analyses will be performed in subgroups by dose treatment arm.

Plasma concentration/time curves will be presented for CPL409116 and M3 in linear and log-linear scale. Curves will be presented separately for Days 1, 8, 57 and 85 for:

- individual subjects (including additional log-linear scale plot showing points used for K_{el} calculation) (PS population),
- arithmetic mean \pm SD within dose cohort, by dose cohort, in linear scale (PSPC population),
- arithmetic mean within dose cohort, by dose cohort, in log-linear scale (PSPC population),

- overlapping individual curves (with mean curve in different color) for each dose cohort, in linear and log-linear scale (PSPC population).

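### The PK parameter set excludes whole patients rather than affected days, so unaffected profiles are lost; separately, no rule covers a profile after post-dose vomiting

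*SAP*

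**What the plan says.** SAP 3.1 defines two PK sets. The PS takes any patient dosed with CPL409116 who has an evaluable PK parameter. PSPC adds that the patient must be "without any major protocol deviation during Treatment Period thought to interfere with the absorption, distribution, metabolism, and excretion of CPL409116". The unit is the patient and the span is the whole Treatment Period. Protocol 10.2 also defines PSPC by patient, but without naming the span.

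SAP 4.13 uses the PS for listings, while "data summaries, plots, and inference analyses will be performed in PSPC population". The secondary PK endpoints in SAP 2.1.2 are "determined on Day 1, 8, 57 and 85", and SAP 4.2.17 derives parameters per subject and day.

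On vomiting, Protocol 6.7 counts a dose as compliant only if all tablets are taken and "administration is without any emesis occurring within 2 hours after IMP administration". SAP 4.2.6 keeps only the tablet condition: "A single dose is to be consider as a compliant when all 4 tablets are administered". Protocol 7.2 uses a different window for withdrawal, when "the subject suffers from moderate or severe emesis within 4 hours in two consecutive IMP administrations". The PK data rules in SAP 4.6 cover missing concentrations, values below LLOQ, and one profile-level case: "If an entire concentration-time profile below LLOQ, the profile will be excluded from the PK analysis".

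**The concern.** The exclusion rule works at a coarser level than the analysis. PK parameters are calculated and tabulated day by day, but a patient enters or leaves every day together. Followed as written, a qualifying deviation on Day 70 takes out a Day 1 profile collected ten weeks earlier, which it cannot have affected. No clause restores the unaffected days.

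Precision is lost in the four daily summaries, the accumulation ratios, the intra-subject variability estimate and the dose-proportionality analyses. The PK parameters are secondary endpoints and exposure-response is a secondary objective. SAP 4.15 already warns that its dose-effect comparisons will have little power.

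The second gap is the missing rule for a profile after emesis. A partly absorbed dose gives measurable but low concentrations, so it need not meet any condition in SAP 4.6. SAP 3.5 lets PK be analysed once all participants have finished treatment, outside the general requirement of a locked and unblinded database. Without a prior rule, the handling of such profiles could be settled with the concentrations already in hand.

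**Working it through.** **Checks on the plan's own figures**
- Doses (SAP 4.2.6): 84 × 2 + 1 = 169. 80% of 169 = 135.2, rounded up to 136. This reproduces the stated 136. Protocol and SAP therefore share the same threshold but define a compliant dose differently.
- PK sampling (Protocol 8.3 and synopsis): 9 + 9 + 2 + 9 + 13 = 42 samples; 42 × 4.5 mL = 189 mL, as stated. Four of the five sampling days give a full profile; Day 29 has two samples.

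**Loss from exclusion by patient**

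Inputs: 25 patients in each of three active arms (SAP 2.2, for example "25 are to be randomized to the treatment arm with CPL409116 at a dose of 60 mg BID"), so 75 patients × 4 full profiles = 300 planned profiles. Let d be the chance that a given PK day is affected by a qualifying deviation. The documents give no value, so d is assumed, with independence between days.
- Removed under the patient rule: 300 × [1 − (1 − d)^4]
- Removed under a patient-day rule: 300 × d
- Share of valid profiles lost to the patient rule: 1 − (1 − d)^3, because a valid profile survives only if the other three days are also clean.

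Results:
- d = 3%: 34 against 9 removed; 1 − 0.97^3 = 8.7% of valid profiles lost.
- d = 5%: 56 against 15 removed, so about 41 of 285 valid profiles; 1 − 0.95^3 = 14.3%.
- d = 10%: 103 against 30 removed, so about 73 of 270 valid profiles; 1 − 0.90^3 = 27.1%.

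For one patient with one affected PK day, three of the four full profiles are lost needlessly. If the affected day is Day 8, 57 or 85, two of the three accumulation ratios were still usable. If it is Day 1, none was. A deviation during home dosing that touches no PK day can cost all four profiles.

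**Vomiting: illustration only**

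If k of 25 profiles in one arm on one day retained a fraction r of their exposure and were left in, the geometric mean would be multiplied by r^(k/25). Both k and r are assumed.
- k = 1, r from 10% to 50%: 0.91 to 0.97
- k = 2, r from 10% to 50%: 0.83 to 0.95

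This shows how much a rule could matter. It does not estimate what will happen.

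**The case against.** The exclusion is narrower than any deviation on any day: it must be major and judged to interfere with absorption, distribution, metabolism or excretion. Such deviations may well span several PK days, for example an interacting medicine or sustained dosing failure. Clustering of that kind would make the loss smaller than independence implies. Nothing disappears from the record, because individual concentrations and parameters are listed for the PS. PK is a secondary and largely descriptive objective. All of this stands and limits the size of the point, but it does not explain why an unaffected day should leave the summaries.

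On vomiting, a reader might infer that the SAP keeps these profiles and so biases exposure downwards, most of all at the dose with most nausea. The documents do not support that:
- No section says such profiles are kept.
- SAP 4.6 already drops a profile wholly below LLOQ.
- Protocol 10.2 foresees listing data excluded from the PK sets with reasons, though it gives no criteria.
- SAP 3.3 leaves deviation classification to a data review plan and meeting, which could class emesis as a deviation. The patient-level rule would then remove all of that patient's days.
- No nausea rates by dose appear in the documents.

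It is equally tempting to take the 2-hour limit in Protocol 6.7 as the PK cut-off. That limit defines dosing compliance, and Protocol 7.2 uses 4 hours for withdrawal. Neither is offered as a test of whether a profile is evaluable.

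**Conclusion.** The patient-level exclusion holds on the text. One affected PK day costs the patient's three other full profiles and any accumulation ratios that were still valid. The overall loss is about 9%, 14% or 27% of valid profiles at assumed rates of 3%, 5% or 10% of PK days, independent between days. The documents supply no rate, so these are a range and not a forecast.

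The vomiting point holds only as an omission: the SAP states no handling for a profile after post-dose emesis, and its compliance definition drops a condition the protocol contains. The direction and size of any bias cannot be derived from the documents. Neither issue touches the primary efficacy analysis.

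**What to change.** - Define PSPC by profile (patient-day). Exclude only the days that a major, ADME-relevant deviation could have affected, and keep the patient's other profiles.
- Before concentrations are released, reconcile Protocol 6.7, Protocol 7.2 and SAP 4.2.6 on emesis. Which window applies is for the sponsor to settle.
- State in the SAP how profiles with post-dose emesis are flagged, and report the PK summaries with and without the flagged profiles.
- Record these decisions at the blinded data review already planned in SAP 3.3, and list each exclusion with its reason, as Protocol 10.2 foresees.

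The cost is SAP wording and sample sizes that vary by day in the PK tables. It also departs from the patient-level PSPC wording in Protocol 10.2, which the CSR should note and justify as Protocol 10 requires. No extra data collection is needed for the patient-day definition.

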3.2. Definition of subgroups

Analysis of primary and secondary endpoints will be provided for ITT and PP populations by the following subgroups:

- Age (<57 years old vs ≥57 years old)

- Sex (male vs. female)
- Disease severity based on DAS28-CRP score at baseline (moderate vs. high).

3.3. Protocol deviations

All protocol deviations will be listed by subject. These deviations will be handled in accordance with the Contract Research Organization's (CRO) SOPs.

For the allocation of patients to analysis populations, all protocol deviations will be reviewed according to the criteria specified below. A comprehensive data review plan, to be finalized before the data review meeting, will detail these criteria and outline all necessary data and listings for an exhaustive assessment of protocol deviations.

The determination of major and minor protocol deviations will be performed during the data review meeting in which key stake-holders will participate. The proceedings and decisions of this meeting will be documented in the data review meeting minutes. This document will be finalized prior to the unblinding of the treatment group for the main analysis of data.

The following protocol violations are defined as major and will thus lead to the exclusion of a patient from the PP population:

Table 2. Protocol deviations

Number	Major protocol deviation	Reasons for exclusion from PP population
1	No valid assessment of DAS28-CRP at Day 1 (Baseline)	X
2	No valid assessment of DAS28-CRP at Day 85 (Week 12)	X
3	Any violation that have a major impact on DAS28-CRP assessment, not limited to in- or exclusion criteria	X
4	Dose or administration of study medication deviates substantially from protocol schedule	X

3.4. Interim analyses

No formal interim analysis is planned.

3.5. Timing of analyses

Data analysis will be performed after all the data will be completed, verified, whole database will be locked and unblinded, with the exception of PK and PD analyses, which will be analysed after the end of the treatment period of all study participants.

4. Statistical analysis specification

4.1. General

Statistical significance level will be equal to 0.05. P-values ≥ 0.001 will be reported to 3 decimal places; p-values less than 0.001 will be reported as " < 0.001 ". The mean, standard deviation, and any other statistics other than quantiles, will be reported to one decimal place greater than the original data. Quantiles, such as median, or minimum and maximum will use the same number of decimal places as the original data. Estimated parameters, not on the same scale as raw observations (e.g. regression coefficients) will be reported to 3 significant figures.

